3.3.4 Pharmacokinetic Outcome Measures

The primary PK outcome measures for this study are as follows:

- PK parameters for MHAA4549A in serum including total exposure (i.e., AUC), maximum observed concentration (C_{max}), clearance, half-life, and volume of distribution, when appropriate, as data allow

The exploratory PK outcome measures for this study are as follows:

- █ [REDACTED]
- █ [REDACTED]

3.3.5 Exploratory Outcome Measures

The exploratory outcome measures for this study are as follows:

- █ [REDACTED]
- █ [REDACTED]
- █ [REDACTED]
 - █ [REDACTED]
 - █ [REDACTED]
 - █ [REDACTED]
- █ [REDACTED]
 - █ [REDACTED]

[REDACTED]

4. MATERIALS AND METHODS

4.1 PATIENTS

This study aims to enroll approximately 334 men and women and is designed to assess the safety and clinical activity of a single IV administration of MHAA4549A in adult patients hospitalized with severe influenza A.

4.1.1 Inclusion Criteria

Patients must meet the following criteria for study entry:

- Hospitalized men or women ≥ 18 years of age on the day of signing the informed consent or obtaining surrogate consent from an authorized representative
- Diagnosis of influenza A where one or both of the following are used as aid(s) in diagnosis:
 - A Sponsor-supplied rapid influenza test
 - A local molecular (PCR) test
- One of the following markers of severity within 24 hours of hospital admission:
 - Requirement for PPV –or–
 - Requirement for O₂ supplementation to maintain SpO₂ > 92%
- A negative urine or serum pregnancy test for women of child-bearing potential
- Patients of reproductive potential must agree to use reliable means of contraception as described below as a minimum (adherence to more stringent local requirements may be required):
 - For female patients: Use of two acceptable methods of contraception throughout the trial, including the active treatment phase AND for 120 day after the last dose of MHAA4549A. Acceptable methods of contraception include: intrauterine device, systemic hormonal contraception (oral or depot), vaginal ring, tubal ligation of the female partner, vasectomy of the male partner, use of latex condoms plus spermicide by the male partner, or cervical cap plus spermicide (where the spermicide could be foam, vaginal suppository, gel, cream, etc.).

Male partners who have had a vasectomy should have the appropriate post-vasectomy documentation available of the absence of sperm in the ejaculate. The vasectomized male partner should be the sole partner for that subject.

- For male patients: Use of condoms *and* refrain from sperm donation until 30 days after dosing.
- Non-reproductive potential is defined below (but could be superseded by local definitions, if they are more stringent):
 - Women who are postmenopausal (i.e., spontaneous amenorrhea for the past year confirmed by an FSH level greater than 40 mIU/mL unless the patient is receiving a hormonal therapy for their menopause)
 - Women who are surgically sterile (i.e., hysterectomy, complete bilateral oophorectomy)
 - Men who are surgically sterile (castration)

4.1.2 Exclusion Criteria

Patients who meet any of the following criteria will be excluded from study entry:

- Pregnant or lactating or intending to become pregnant during the study
 - Women who are not postmenopausal (≥ 12 months of non-therapy-induced amenorrhea) or who are not surgically sterile must have a negative urine or serum pregnancy test result within 2 days prior to study treatment.
- *Hypersensitivity to monoclonal antibodies or to the active substance or any excipients of MHAA4549A study drug*
- *Hypersensitivity to the active substance or to any excipients of oseltamivir*
- Investigational therapy within the 30 days prior to study treatment
- Received prior therapy with any anti-influenza monoclonal antibody therapy including MHAA4549A 8 months prior to study treatment
- Current treatment (within 7 days of dosing) with amantadine or rimantidine
- Patients who have taken more than a total of 3 days (6 doses) of approved anti-influenza therapy (e.g., oral oseltamivir, inhaled zanamivir, or oral ribavirin) in the period from onset of symptoms and prior to enrollment
- Admission > 48 hours prior to study treatment
- Onset of influenza symptoms > 5 days prior to study treatment
- Positive influenza B or influenza A+B infection within 2 weeks prior to study treatment
- High probability of mortality in the next 48 hours as determined by the investigator
- Patient requiring home or baseline oxygenation therapy
- Patient with history of chronic lung disease resulting in baseline $SpO_2 < 95\%$

- Patient on a chronic dose of corticosteroids exceeding 10 mg/day of prednisone or equivalent steroid dose for a duration of greater than 14 days within 30 days of entry into study
- Patients with the following significant immune suppression:
 - Bone marrow or solid organ transplant in the previous 12 months
 - Cancer chemotherapy in the previous 12 month
 - HIV infection with most recent CD4 < 200 cells/mL
 - Other significant immune suppression as determined by the investigator in discussion with the Sponsor Medical Monitor or representative
- Patient on extracorporeal membrane oxygenation (ECMO) at time of randomization
- Any disease or condition that would, in the opinion of the site investigator or Sponsor, place the subject at an unacceptable risk of injury or render the subject unable to meet the requirements of the protocol

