APPENDIX 1a (cont'd)

Schedule of Assessments: Hospitalization Days

- ^o Complete physical examination includes evaluations of general appearance of head, eye, ear, nose, and throat, cardiovascular, dermatological, musculoskeletal, respiratory, gastrointestinal, genitourinary, and neurological systems. Changes from any prior examination should be recorded. New or worsened abnormalities should be recorded as adverse events, if appropriate.
- ^p Limited, symptom-directed physical examination includes, at a minimum, evaluation of general appearance, dermatological examination of the injection sites, evaluations directed by patient-reported symptoms, and any other evaluations that the investigator deems clinically relevant. Changes from any prior examination should be recorded. New or worsened abnormalities should be recorded as adverse events, if appropriate.
- ^q Height will be obtained at screening only. Weight will be obtained at all indicated visits. Height and weight will be recorded in centimeters and kilograms, respectively.
- ^r Local laboratory measurements should be utilized.
- ^s Urinalysis includes pH, specific gravity, glucose, protein, ketones, blood, bilirubin, nitrite, and leukocyte esterase. Microscopic examination (e.g., sediment, RBCs, WBCs, casts, crystals, epithelial cells, bacteria) will be performed if clinically indicated.
- ^t [REDACTED]
- ^v Day 1 serum PK samples are to be drawn 30 (\pm 5) minutes pre-dose of MHAA4549A, 60 (\pm 15) minutes after the end of infusion. PK samples will be drawn from the contralateral arm from that used for drug infusion and must be labeled with the exact time of draw.
- ^w [REDACTED]
- ^x If patient is discharged on or before Day 5, the oseltamivir PK sample should be taken on the discharge day.
- ^y [REDACTED]
- ^z Assessment to be conducted based on entry into ICU; may vary from patient to patient.
- ^{aa} For optional thyroid stimulating hormone test.
- ^{bb} HIV serology result not needed for randomization.
- ^{cc} Patients who are discharged from the hospital with oseltamivir will be required to complete a medication diary and return the medication diary, empty (used) oseltamivir packets and unused oseltamivir capsules to the study site at the next follow up visit. Patients will record the date and time when each oseltamivir capsule is administered.

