*Lymphocytes Decrease – cell/mm ³	750 – 1,000	500 – 749	250 – 499	<250
*Eosinophils – cell/mm ³	650 – 1500	1501 – 5000	>5000	Hypereosinophilic
Abnormal Fibrinogen	Low: 100 – 200 mg/dL High: 400 – 600 mg/dL	Low: <100 mg/dL High: >600 mg/dL	Low: <50 mg/dL	Fibrinogen associated with gross bleeding or with disseminated coagulation
Fibrin Split Product	20 – 40 mcg/mL	41 – 50 mcg/mL	51 – 60 mcg/mL	>60 mcg/mL
Prothrombin Time (PT)	1.01 – 1.25 x ULN	1.26 – 1.50 x ULN	1.51 – 3.0 x ULN	>3 x ULN
Activated Partial Thromboplastin Time (APTT)	1.01 – 1.66 x ULN	1.67 – 2.33 x ULN	2.34 – 3 x ULN	>3 x ULN
Methemoglobin	5.0 – 9.9%	10.0 – 14.9%	15.0 – 19.9%	>20.0%

From the FDA Guidance document 'Toxicity Grading Scale from Healthy Adult and Adolescent Volunteers Enrolled in Preventative Vaccine Clinical Trials'

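### As written, the HIV exclusion limit of 200 CD4 cells per mL is 0.2 cells/mm³, so read literally this item excludes essentially no HIV patient; the unit needs to be reconciled

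*Combined protocol and SAP*

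**What the plan says.** Section 4.1.2 (Exclusion Criteria) has a sub-list headed "Patients with the following significant immune suppression". One of its items is "HIV infection with most recent CD4 < 200 cells/mL". The synopsis repeats the item with the same number and unit. This is so in the original protocol, in Version 2 and in Version 3 (VHP Only), which makes six lists. Nowhere in the supplied text is a CD4 limit given in another unit.

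Two other exclusions bear on the same patients. The next item in the sub-list is "Other significant immune suppression as determined by the investigator in discussion with the Sponsor Medical Monitor or representative". The last exclusion in Section 4.1.2 lets the investigator or sponsor refuse anyone whose condition would put them at undue risk.

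The hematology table of Appendix 9 (visible in Versions 2 and 3) has the row "Lymphocytes Decrease – cell/mm ³", running from 750–1,000 for Grade 1 to below 250 for Grade 4. Neutrophils, platelets and white cells are also graded per mm³.

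No CD4 count appears in the laboratory tests of Table 3 or Table 4. HIV serology is drawn at screening, but Appendix 1a of Versions 2 and 3 adds the footnote "HIV serology result not needed for randomization".

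**The concern.** The item is one of the objective entries in a list meant to keep out patients with marked immune suppression. In the printed unit the limit lies so close to zero that it cannot do that job, and it does not match the unit the protocol uses for blood cells elsewhere.

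What is at stake is eligibility. Section 4.6.1 requires sites to confirm every criterion before randomization, and Section 6.2 has eligibility exceptions summarized by treatment group. Because the protocol schedules no CD4 test, this item is applied by comparing an existing result with the printed number. If that number carries the wrong unit, enrolling an HIV patient with a very low CD4 count is not an exception to this criterion, and the Section 6.2 summary would not show it as one.

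**Working it through.** There is no derived figure in the plan to reproduce. The check is a unit conversion and a comparison of places.

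**Inputs**
- Limit: 200 cells/mL (synopsis and Section 4.1.2, all three versions).
- Unit used for lymphocytes: cells per mm³ (Appendix 9, hematology table).
- Conversion: 1 mL = 1 cm³ = 10 × 10 × 10 mm³ = 1,000 mm³.

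**Step 1. The limit in the Appendix 9 unit.**
200 cells/mL ÷ 1,000 = 0.2 cells/mm³.

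**Step 2. The same number carried in the Appendix 9 unit, for scale only.**
200 cells/mm³ × 1,000 = 200,000 cells/mL. The ratio to the printed limit is 200,000 ÷ 200 = 1,000.

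**Step 3. Who meets the item as printed.**

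| CD4 count (cells/mm³) | Same count (cells/mL) | Below 200 cells/mL? |
|---|---|---|
| 1 | 1,000 | No |
| 10 | 10,000 | No |
| 50 | 50,000 | No |
| 100 | 100,000 | No |
| 199 | 199,000 | No |

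If counts are reported as whole numbers per mm³ (an assumption), only a result of 0 meets the item.

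**Step 4. An illustration in total lymphocytes.** Suppose CD4 cells make up 5% to 40% of lymphocytes; this range is assumed and is not in the documents. A patient at the printed limit would then have total lymphocytes of 0.2 ÷ 0.05 = 4 cells/mm³ at one end and 0.2 ÷ 0.40 = 0.5 cells/mm³ at the other. The lowest band in Appendix 9 starts below 250 cells/mm³. The conclusion does not depend on the assumed share.

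**Step 5. Is it an isolated slip?** All six lists agree, so the supplied text contains no correct copy to defer to. The change summaries for Versions 2 and 3, and the Version 4 items that are visible, mention no change to CD4.

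**The case against.** The strongest reply is that little follows in practice. Several parts of it stand.

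- **The item is not the whole screen.** A reader might infer that HIV patients with profound immune suppression would pass screening. The documents do not support that. They would pass this one item, but the discretionary immune-suppression exclusion and the undue-risk exclusion can still keep them out. Both rest on judgement, so they soften the consequence without repairing the criterion.
- **Sites may apply the intended rule anyway.** The CD4 result is an existing one, read in the reporting laboratory's own unit. Many sites may therefore apply a sensible reading. They would then be applying a rule the protocol does not state, but the harm would be smaller.
- **No programmed check is described.** A reader might picture an edit check coded in cells/mL that lets such patients through. No section mentions one, so it is only something to look for.
- **Undiagnosed HIV is a separate gap.** Since the serology result is not needed for randomization, HIV not already known at entry could be missed whatever the CD4 unit.
- **Appendix 9 sets no CD4 rule.** It grades changes in total lymphocytes. Its Grade 4 limit of 250 cells/mm³ is 250,000 cells/mL, which is 1,250 times the printed CD4 limit, but that ratio compares different cell populations used for different purposes. Appendix 9 is evidence of the unit convention and no more.
- **The unit might be a misprinted micro sign.** That is possible, but the micro sign prints correctly in the filter size in Section 4.3.2.1, and the same unit recurs in all six lists. Either way the text needs correcting.

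What remains is that the criterion, as printed, does not do what its heading says.

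**Conclusion.** The point holds as a unit error in an eligibility threshold. Read literally, the item sets 0.2 cells/mm³, a factor of 1,000 below the same number in the unit of Appendix 9, and it excludes essentially no HIV patient. This rests on exact unit conversion and on text that is identical in six lists.

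The size of the consequence cannot be stated. The documents give no number of HIV patients expected or enrolled, and the discretionary exclusions and site practice may make it small. Sample size, power and alpha are unaffected.

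Two stronger inferences should be avoided. One is that the error adds material heterogeneity to the primary or virology endpoints: the documents give nothing on how such patients recover or how many there would be, and randomization gives no reason to expect bias between arms. The other is that the error stands in the global protocol now in force. The exclusion lists seen end with Version 3 (VHP Only). Only the opening pages of Version 5 (Global) are present, and the full Version 4 (Russia Only) list is not shown, although its rationale says that exclusion criteria were updated. The unit may or may not persist there.

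**What to change.** Reconcile the CD4 unit in the synopsis and in Section 4.1.2 with the per-mm³ convention of Appendix 9, and carry the correction into any eligibility checklist or electronic check built from them. The sponsor should confirm the intended threshold; the documents do not settle it. The sponsor should also check whether the Version 4 and Version 5 (Global) exclusion lists carry the same unit.

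The cost is negligible: one unit in two places per version, made with the next amendment or as a clarification to sites. No analysis, sample size or visit schedule changes.

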For regulatory reporting purposes, and if required by local health authorities, the Sponsor will break the treatment code for all suspected unexpected serious adverse reactions (SUSAR)(see [Section 5.6](#)) that are considered by the investigator or Sponsor to be related to study drug.

4.3 STUDY TREATMENT

4.3.1 Formulation, Packaging, and Handling

4.3.1.1 MHAA4549A and Placebo

MHAA4549A, matching placebo, and up to 10-day supply of oseltamivir (Tamiflu®) will be supplied by the Sponsor. For information on the formulation, packaging, and handling of MHAA4549A and placebo; see the Pharmacy Manual and the MHAA4549A Investigator's Brochure.

The MHAA4549A vial delivers 10 mL (500 mg) of drug product solution, but may contain more (approximately 10.3 mL) than the stated volume to enable delivery of the entire 10 mL volume. MHAA4549A is formulated as 50 mg/mL in 10 mM sodium succinate, 240 mM sucrose, and 0.02% (w/v) polysorbate 20 at pH 5.5 and is contained in a 15 mL forma vitrum (USP/PH. Eur. Type 1) glass vial. The drug product is suitable for single use only and contains no preservatives.

Placebo for MHAA4549A has the same composition as the drug product (without MHAA4549A) and is supplied in an identical vial configuration. The placebo contains no preservatives and is suitable for single-use only. Placebo is formulated as 10 mM sodium succinate, 240 mM sucrose, and 0.02% polysorbate 20 at pH 5.5 in a total volume of 10 mL in a 15 mL forma vitrum (USP/PH. Eur. Type 1) glass vial.

MHAA4549A and placebo are supplied in identical blinded vials labeled with unique kit numbers. IxRS will assign kit numbers for each treatment arm; all treatment arms will be assigned the same total number of vials for each treatment, and the same preparation instructions. Placebo is identical to active MHAA4549A in formulation and appearance but does not contain active drug substance.

4.3.1.2 Oseltamivir (Tamiflu)

Oseltamivir (Tamiflu) is an influenza NAI indicated for treatment of acute, uncomplicated influenza. For information on the formulation, packaging, and handling of oseltamivir; see the local prescribing information for oseltamivir.

Storage: Capsules should be stored at 25°C (77.7°F); excursions permitted to 15° to 30°C (59° to 86°F).

4.3.2 Dosage, Administration, and Compliance

4.3.2.1 MHAA4549A and Placebo

The randomization of patients will be managed by a central IxRS. All patients will be randomly assigned to receive either a single dose of MHAA4549A 3600 mg IV or placebo IV at a 1:1 ratio. Oseltamivir will be dispensed via IxRS. Oseltamivir dosing is described in [Table 2](#).

Administration of MHAA4549A or placebo will be performed in a setting with emergency medical equipment and personnel who are trained to monitor for and respond to medical emergencies. A qualified physician will be on site during study drug administration for all patients.

A single dose of MHAA4549A or placebo will be delivered by IV infusion following dilution in 0.9% normal saline over approximately 60 minutes. Study drug should be delivered using a 0.22 µm in-line filter. Compatibility testing has shown that MHAA4549A is stable when diluted in 0.9% normal saline in a polyvinylchloride, polyolefin bag, or ethylene vinyl acetate bag (EVA), at or above a combined total concentration of 0.24 mg/mL up to 27.0 mg/mL. Study drug must be administered within the treatment window outlined in [Section 3.1.1](#). Further detailed instructions for preparation of study drug can be found in the Pharmacy Manual.

There are no recommended dosage modifications for MHAA4549A since it is a single infusion. Any overdose or incorrect administration of study drug should be noted on the Study Drug Administration electronic Case Report Form (eCRF). Adverse events associated with an overdose or incorrect administration of study drug should be recorded on the Adverse Event eCRF. General supportive measures will be taken to manage any AEs associated with overdose. Patients experiencing such AEs will be followed up clinically until the event has resolved.

Trained clinical site staff responsible for adequate and accurate study drug administration, accounting, and management will administer study drugs to patients. Study drug preparation and dosing instructions will be provided to each site. The exact times of study drug administration will be recorded in the relevant dispensing/administration logs and patient's source notes. Any noncompliance or problems with study drug administration will be recorded in the patient's source notes and reported to the Sponsor if appropriate.

4.3.2.2 Oseltamivir-Neuraminidase Inhibitor (NAI)

The Sponsor will be providing oseltamivir (Tamiflu®) for this study for up to a 10-day course. Dosage and administration should follow local prescribing information for oseltamivir. Either 75 mg or 150 mg of oseltamivir will be administered twice daily as described in [Table 2](#). Capsules can be opened and the granules administered via nasogastric tube, if required.

Guidelines for dosage modification for renal dosing are presented in [Table 2](#).

Any overdose or incorrect administration of oseltamivir should be noted on the oseltamivir Administration eCRF. Adverse events associated with an overdose or incorrect administration of oseltamivir should be recorded on the Adverse Event eCRF.

Patients who are discharged from the hospital with oseltamivir will be required to complete a medication diary and return the medication diary, empty (used) oseltamivir packets and unused oseltamivir capsules to the study site at the next follow up visit. Patients will record the date and time when each oseltamivir capsule is administered.

4.3.3 Investigational Medicinal Product Accountability

Investigational medicinal products (IMPs) required for completion of this study (i.e., MHAA4549A and oseltamivir) will be provided by the Sponsor. The study site will acknowledge receipt of IMPs and confirm the shipment condition and content. Any damaged shipments will be replaced.

The IMP will be stored in a secure pharmacy or locked area with access limited to authorized personnel, in accordance with the details provided in the Investigator's Brochure and Pharmacy Manual. Upon receipt, MHAA4549A and placebo vials must be refrigerated at 2°C to 8°C until use. MHAA4549A does not contain antimicrobial preservatives; therefore, care must be taken to ensure that the solution for infusion is not microbiologically compromised during preparation. Dilute under appropriate aseptic conditions using 0.9% normal saline. The solution for infusion should be used immediately. If not used immediately, in-use storage times and conditions prior to use should not exceed 24 hours at 2 to 8°C and/or 4 hours at ambient temperature (18°C–24°C). If the dose solution is stored at 2°C–8°C, it should be removed from refrigeration and allowed to reach room temperature prior to administration. If the infusion is interrupted and the combined ambient temperature storage and interruption time exceeds 4 hours, prepare a new dose solution to resume the infusion (see the Pharmacy Manual). Protect dose solutions from heat and intense light.

The total duration from the preparation of dose solutions to the end of infusion should not exceed 24 hours. Vials are intended for single use only; therefore, any remaining solution should be discarded (see the Pharmacy Manual).

IMPs will either be disposed of at the study site according to the study site's institutional standard operating procedure or returned to the Sponsor or their delegate with the appropriate documentation. The site's method of IMP destruction must be agreed to by the Sponsor. The site must obtain written authorization from the Sponsor before any IMP is destroyed, and IMP destruction must be documented on the appropriate form.

Accurate records of all IMPs received at, dispensed from, returned to, and disposed of by the study site should be recorded on the Drug Inventory Log.

